#### 1. PROTOCOL INFORMATION

*Title: Efficacy of broad spectrum antibiotics combined with oral steroids versus antibiotics alone in the treatment of chronic rhinosinusitis (CRS) in adults without nasal polyposis (CRSsNP)*

*Funding Source: None.*

*Phase of Study: Phase 4*

*Version Date of Protocol: 12/3/2020*

#### 4. STUDY INFORMATION

*Location(s) of Research Activity: Loma Linda Sinus and Allergy Center*

*Expected Start/Stop Dates of Research: Start upon IRB approval, will plan to conduct study and collect data over 12 months*

*Special Time Sensitivities: None*

*Type of Research: Interventional*

#### 5. INCLUSION / EXCLUSION CRITERIA

*Inclusion Criteria:*

- 1. They have three-months of persistent symptoms meeting criteria for chronic rhinosinusitis as defined by the Taskforce on Rhinosinusitis.*
- 2. They have a CT-scan in our clinic or have a viewable recent (< 3weeks prior to clinic visit) CT-scan with a Lund Mckay score of 6 or greater. A Lund Mckay score of 6 or greater is felt to be indicative of at least moderate CRS.*
- 2*
- 3. They do not have nasal polyps on initial clinic nasal endoscopy*
- 4. They are willing to participate in a clinical study*
- 5. They are between the ages of 18 to 80.*

*Exclusion Criteria:*

- 1. They have a condition in which the use of systemic corticosteroids is contraindicated such as diabetes will be excluded.*
- 2. They are unable to or unwilling to take the prescribed antibiotics or steroids will be excluded.*
- 3. They have been treated with a > 3 week course of antibiotics and/or systemic steroids will also be excluded.*
- 4. They have variants of chronic sinusitis known to be refractory to medical therapy such as Wegener's granulomatosis, primary ciliary dyskinesia or sarcoidosis.*
- 5. They have sinusitis secondary to prior surgery, a dental procedure or anatomical variants.*
- 6. They have nasal polyps on physical exam.*
- 7. They are pregnant. Subjects who are possibly pregnant will be excluded based on history. Pregnancy testing is not standard of care for diagnostic imaging.*
- 8. They have a Lund-Mckay score on CT scan of < 6*
- 9. They are < 18 or > 80 years old*

**6. SUBJECT RECRUITMENT & SCREENING**

*Number of Subjects: ~40*

*Subject Age Range: ≥18 years of age, ≤80 years of age*

*Subject Gender: Both*

*Racial/Ethnic Distribution: Any*

*Target Study Population: Patients without nasal polyps who suffer from chronic rhinosinusitis.*

*English/Non-English Speaking Subject Info: Translators will be provided for non-English speaking patients*

*Certified Translated Consent Form Use: None*

*Recruitment Material Type Info: All patients who present to Loma Linda Sinus and Allergy center meeting inclusion criteria will be asked to participate*

*Vulnerable Subject Info: N/A*

*Recruitment Method Info: Patients without nasal polyps as documented by endoscopy and who are not currently taking antibiotics or nasal/oral corticosteroids will be prospectively recruited. This will be a randomized blinded study. Patients will be randomized into three groups- Group 1 will received oral antibiotics (Bactrim or Augmentin) nasal steroid sprays (fluticasone) along with nasal saline irrigation , Group 2 will receive oral antibiotics, steroid nasal spray and in addition oral steroids (prednisone) at a tapered dosage for 6 days, and Group 3 will receive oral antibiotics, steroid nasal spray and in addition oral steroids at a tapered dosage for 20 days. The investigator will be blinded as to which group the subjects are placed.*

*Description of consent precautions regarding subject rights and welfare: Informed consent will be obtained from all patients after they have been given the opportunity to have their questions answered.*

*Pregnancy Status Info: Pregnant patients will not be included in study*

3

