7. INFORMED CONSENT PROCESS

*Specific description of informed consent process: Informed consent will be obtained from all participating subjects prior to enrollment in the study. (See attached informed consent form) The risks, benefits and alternatives will be discussed with potential subjects by clinic investigators listed above (Drs. [name], [name] and [name]) at time of appointment at Loma Linda Sinus and Allergy center. Patient information will be kept private and there will be time for decision-making/discussion prior to enrollment in the study. Patient who are able to verbalize/demonstrate their understanding and are able to give informed consent will be considered. Subjects will be identified by state ID or Driver's license and will be randomized into one of two study groups by flip of a coin.*

*Coding system: diagnosis and office visits will be coded in the standard fashion.*

*Privacy of Medical and Research Records information/medical records: Patient information and study data will be kept as hard copy by PI in locked desk/room and some study data will be kept on encrypted/protected flash drive by PI.*

*Medical Release forms, HIPAA compliance/authorization form: See attached form*

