*1. At the time of enrollment nasal endoscopy will be performed to confirm that the patient does not have evidence of nasal polyps. Office-based sinus CT scan will also be completed on initial visit. Lund-McKay score at initiation of treatment will be one a determinate of study eligibility. (Lund-McKay staging system is currently the most widely accepted system to radiographically characterize and diagnose CRS. A score of 6 or greater indicates significant sinus disease and meets inclusion criteria for study. See below table 1 for Lund-McKay staging system.) Note: Endoscopy and CT of paranasal sinuses are the standard of care for evaluation of patients with symptoms of CRS and will be offered to all patients presenting with these symptoms regardless of study enrollment status.*

*2. Subjects will be asked to fill out a SNOT 22 survey before the start of therapy.*

*(SNOT 20 form attached).*

*3. Nasal endoscopy score will also be obtained during initial visit. (Nasal endoscopy scoring form attached). This exam is part of the standard of care.*

*4. Subjects will be randomized into 3 groups via an electronic random generator (see below)*

*1. Group 1: Treated with oral antibiotics, nasal steroid spray and saline rinses for 3 weeks (standard of care)*

*2. Group 2: Treated with above + Prednisone 6 day tapered dosage (standard of care)*

*3. Group 3: Group 2: Treated with above + Prednisone 20 day tapered dosage (standard of care)*

*4. Random generator:*

*5*

*5. Patients will return to office at 4 weeks (following 3 weeks of oral antibiotics, nasal steroid spray, nasal saline irrigation + prednisone for patients in Groups 2 and 3), At that time, patients will be asked to fill out SNOT 22 survey, nasal endoscopy and CT scan to assess response to treatment. (standard of care).*

*6. At the 4 week follow up, patients will be asked to fill out SNOT 22 survey, and undergo nasal endoscopy. (standard of care).*

*d. Alternative procedures, if any, that are not included in the study but might be advantageous to the subject - None*

*e. If any deception is required for validity of this study, explain why this is necessary and how subject(s) will be debriefed. - None*

*f. Concise review of literature that supports the rationale, objectives, and methodology of the proposed study.*

*1. Chronic sinus infections (chronic sinusitis or CRS) are common conditions that affect millions of Americans. This disease can be divided*

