## 9. DATA COLLECTION

*As above. The data which will be collected is clinic nasal endoscopy score, visual analogue score (VAS), SNOT 20 score and initial CT of paranasal sinuses with Lund7*

*McKay score. Response to treatment as recorded by subjective scoring systems above will be recorded in hard copy and be kept by PI in secure, locked drawer.*

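### The trial is called blinded, but only the investigator is masked: patient-completed scores are open-label, and the 4-week CT, the outcome easiest to read masked, is missing from the data list

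*Protocol*

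**What the plan says.** Section 6 (Recruitment Method Info) states "This will be a randomized blinded study". After describing the three groups, the same paragraph adds "The investigator will be blinded as to which group the subjects are placed". Nothing in the protocol says that patients are masked.

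Sections 6 and 8 give Group 1 antibiotics, nasal steroid and saline without oral steroid. Group 2 adds a 6-day prednisone taper and Group 3 a 20-day taper. The drug list in Section 8(h) contains fluticasone, Augmentin or Bactrim, the two tapers and saline. It has no placebo or dummy taper.

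On outcomes, Section 8(c) has subjects complete a SNOT survey before therapy and at 4 weeks. Step 5 has endoscopy and CT at the 4-week visit. Step 6, for the same visit, has SNOT and endoscopy only. Section 9 lists the endoscopy score, VAS, SNOT and the initial CT with its Lund-Mackay score, and continues: "Response to treatment as recorded by subjective scoring systems above will be recorded in hard copy".

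**The concern.** In an add-on comparison without placebo, the patient can tell which group he or she is in. On a questionnaire the patient completes, the patient is also the assessor. If patients given oral steroid expect to do better and report accordingly, SNOT will favour prednisone even when the drug adds nothing. Masking the investigator does not touch this.

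Two things make it matter here. First, the unqualified word in Section 6 may be carried into a report and lead readers to discount the bias. Second, a radiological score could be read without knowledge of group or visit, yet Section 9 does not list it after baseline. Section 13 says the study will show whether adding oral steroids is efficacious. As the data list stands, that conclusion would rest on open-label patient reports and on an endoscopy score for which no masking procedure is described.

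**Working it through.** **Step 1. Who is masked, outcome by outcome.**

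| Outcome | Who produces it | Protection from investigator masking |
|---|---|---|
| SNOT (Sections 8, 9) | Patient, who knows the treatment | None |
| VAS (Section 9) | Not stated; ordinarily the patient | None if patient-rated |
| Endoscopy score (Sections 8, 9) | Clinician | Some, if the scorer stays masked |
| 4-week CT (Section 8, step 5 only) | Reader of the scan | Can be complete if de-identified, but the score is not in Section 9 |

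**Step 2. Is the 4-week CT collected?** Step 5 of Section 8(c) includes it as a measure of response. Step 6, for the same time point, does not mention it. Section 9 begins by referring back to what came before, then names only the initial CT. The protocol therefore leaves open both whether every patient has the scan and whether its score is recorded.

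**Step 3. How large could the effect be?** The protocol states no bias, test or significance level, so there is no figure to reproduce. What follows is illustrative.

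Inputs:
- About 40 subjects (Section 6). Equal allocation gives 40/3 = 13.3, so about 13 per group. Groups 2 and 3 together have about 27.
- Assumed: two-sided 5% t-test, no true effect, and a reporting bias *b* of 0.2 to 0.4 SD in favour of prednisone.

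Formula: the noncentrality is δ = b / √(1/n₁ + 1/n₂), with n₁ + n₂ − 2 degrees of freedom. The error rate is the probability that a noncentral t variable falls outside ± the critical value.

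- 13 vs 13: √(1/13 + 1/13) = 0.392, df = 24, critical value 2.064.
  - b = 0.2: δ = 0.510, error rate 7.8%.
  - b = 0.4: δ = 1.020, error rate 16.5%.
- 13 vs 27 (Group 1 against Groups 2 and 3 pooled): √(1/13 + 1/27) = 0.338, df = 38, critical value 2.024.
  - b = 0.2: δ = 0.592, error rate 8.9%.
  - b = 0.4: δ = 1.185, error rate 21.1%.

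Any bias other than zero gives an error rate above 5%. Only the amount depends on the assumption.

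**The case against.** The best reply is that the label is qualified within its own paragraph. The text does not use the term double-blind and names the investigator as the masked party, so a careful reader is not misled. That stands: the label is loose, and the protocol makes no false claim that patients are masked.

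A reader might also infer that blinding protects nothing in this trial. The documents do not support that. Endoscopy heads the Section 9 list and is scored by a clinician, so masking, if kept, has value there.

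Nor does Section 9 show that response is defined by subjective scores alone or that the 4-week CT is discarded. The quoted sentence is about how scores are recorded and stored, the scoring systems it refers back to include endoscopy, and the section points back to Section 8. The omission is an inconsistency to be reconciled.

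A third tempting inference is that investigators are unmasked at consent, because Section 7 says subjects "will be randomized into one of two study groups by flip of a coin". Section 7 does not say who flips the coin or learns the result. The sentence conflicts with the three groups and electronic generator of Section 8, which is mainly a separate contradiction about randomization. What remains for blinding is that no passage says how allocation is kept from the person who scores endoscopy.

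Finally, the error rates rest on an assumed bias and on comparisons the protocol does not specify, so they do not measure this trial's error rate. Leaving out a placebo is an understandable choice in an unfunded study of about 40 patients at one clinic.

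**Conclusion.** The point holds in a limited form. The unqualified label in Section 6 covers a design in which only the investigator is masked. SNOT, and VAS if patient-rated, are open-label measures. Endoscopy has partial protection that depends on an undescribed procedure. The 4-week CT, the outcome best suited to masked reading, is inconsistently specified and absent from the data list.

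If patients' knowledge shifted reported scores by 0.2 to 0.4 SD, a nominal 5% error rate would become roughly 8–17% for one pairwise comparison, or 9–21% for pooled prednisone against none. This assumes equal allocation of 40, a two-sided 5% t-test and no true effect. The direction follows from the design; the size is an assumption.

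The correction is worth making before enrolment. A statistical analysis plan could not restore masking or recover a score that was never recorded.

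**What to change.** - **Section 6:** describe the trial as *randomized, investigator/outcome-assessor-blinded, open to patients*.
- **Sections 8(c) and 9:** reconcile steps 5 and 6 with the data list. Where the 4-week CT is taken, add its Lund-Mackay score to the data collected.
- **Reading of scans:** have baseline and 4-week scans read de-identified and in random order by an existing investigator who did not see that patient.
- **Allocation:** keep it away from whoever scores endoscopy, and say how.
- **Reporting:** present SNOT and VAS as open-label outcomes beside the masked CT score. State in Section 9 who completes the VAS.

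The cost is a less favourable label and a little reading time for existing staff. No placebo or extra visit is needed. No extra scan is needed either, provided the score is recorded only where the reconciled protocol already takes one.

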## **8. STUDY DESIGN**

*a. Background or rationale for this study: Chronic sinus infections (chronic sinusitis or CRS) are common conditions that affect millions of Americans. This disease can be divided into two main patient groups: Patients with chronic rhinosinusitis without nasal polyps (CRSsNP) and those with nasal polyps (CRSwNP). We will be focusing on the non-polyp group. While this is a common disorder, medical treatments for this condition vary considerably and little is known how and why different treatments work in some individuals and not in others. Topical nasal steroids and oral antibiotics are the mainstay and standard of care for both CRSsNP and CRSwNP. Oral steroids are commonly given for both of these sinusitis variants, however their role in non-polyp CRS patients is less well delineated. The purpose of this research study is to better*

*understand whether orally administered steroids results in superior results when compared with nasally sprayed steroids in this population. The investigators will compare patients with chronic sinusitis who are treated with antibiotics, topical nasal sprayed steroid therapy, and compare them to chronic sinusitis patients who receive antibiotics and nasally sprayed steroid therapy along with a short course or long course of oral steroids. The goal is to determine if oral steroids have a role in CRSsNP, and if so, the most effective dosage.*

*b. Objectives. To compare the effectiveness of topical nasal steroid sprays, oral antibiotics and saline nasal irrigations versus topical nasal steroids, oral antibiotics, saline nasal irrigation + oral corticosteroids (prednisone) in CRS patients without nasal polyps.*

*c. Procedures involved (Research Interventions). Chronological order of all research interventions, distinguishing standard of care vs. research intervention:*

*4*

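### Does Section 6 leave nasal saline irrigation out of the two prednisone groups?

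*Protocol*

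**What the plan says.** The protocol describes treatment group by group in two places.

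The first is the recruitment-method entry of Section 6. Group 1 receives oral antibiotics and "nasal steroid sprays (fluticasone) along with nasal saline irrigation". The second arm is described as "Group 2 will receive oral antibiotics, steroid nasal spray and in addition oral steroids (prednisone) at a tapered dosage for 6 days". Saline is not mentioned there. The wording for the third arm follows the same pattern, again without saline: "Group 3 will receive oral antibiotics, steroid nasal spray and in addition oral steroids at a tapered dosage for 20 days".

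The second is step 4 of Section 8c, under a heading that promises "Chronological order of all research interventions, distinguishing standard of care vs. research intervention". Its entries are:

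- for the first arm, "Group 1: Treated with oral antibiotics, nasal steroid spray and saline rinses for 3 weeks (standard of care"
- for the second arm, which refers back to the first, "Group 2: Treated with above + Prednisone 6 day tapered dosage (standard of care"
- for the third arm, in the same form, "Treated with above + Prednisone 20 day tapered dosage (standard of care"

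Saline also appears in three other places:

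- The objective in 8b sets "topical nasal steroid sprays, oral antibiotics and saline nasal irrigations versus topical nasal steroids, oral antibiotics, saline nasal irrigation + oral corticosteroids (prednisone".
- Step 5 of 8c, on the four-week visit, lists antibiotics, spray and saline irrigation as the preceding treatment, with prednisone for Groups 2 and 3.
- The drug list in 8h ends with nasal saline to be used at liberty and does not link it to any group.

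The title and the rationale in 8a do not mention saline for any arm.

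**The concern.** Silence on saline in the title or in 8a means little, because it applies to every arm alike. Section 6 looks different. In a single sentence it names three shared treatments for Group 1, repeats two of them for Groups 2 and 3, and drops the third. Prednisone is then said to be given in addition, and the list just before those words holds only antibiotics and spray. Section 6 is also the first place where randomization and treatment by group are set out, and the protocol has no rule saying which section governs when two differ.

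The central comparison is at stake. The objective in 8b is to compare background treatment with the same background plus prednisone. If staff took Section 6 as the arm definition and gave no saline to Groups 2 and 3, every comparison with Group 1 would mix the effect of adding prednisone with the effect of removing saline. No analysis could separate the two, because the components would be perfectly confounded by design.

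**Working it through.** There is no figure to reproduce, so the check sets the arm descriptions side by side.

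| Source | Group 1 | Group 2 | Group 3 |
|---|---|---|---|
| Section 6 | saline named | not named | not named |
| 8b objective | saline named | saline named (prednisone side) | saline named (prednisone side) |
| 8c step 4 | saline named | carried over from the entry above | carried over from the entries above |
| 8c step 5 | saline named | saline named | saline named |
| 8h drug list | no group given | no group given | no group given |
| Title, 8a | not named | not named | not named |

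**Components separating the arms.** Write A for antibiotics, S for spray, I for saline irrigation, P6 and P20 for the two prednisone courses.

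- Under 8c: Group 1 = {A, S, I}, Group 2 = {A, S, I, P6}, Group 3 = {A, S, I, P20}. Groups 2 and 3 each differ from Group 1 in one component, prednisone.
- Under Section 6 with silence read as exclusion: Group 1 = {A, S, I}, Group 2 = {A, S, P6}, Group 3 = {A, S, P20}. Groups 2 and 3 each differ from Group 1 in two components, prednisone and saline.
- Group 2 against Group 3 differs only in the prednisone course under either reading, so that comparison is not affected.

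**Is silence in Section 6 an exclusion?** Three features of the text speak against it.

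1. The sentence shortens as it goes. The antibiotics and the spray are identified by name for Group 1 only, and the oral steroid is identified as prednisone for Group 2 but not for Group 3. Nobody would infer a different antibiotic, spray or oral steroid from that.
2. The entry gives no doses and no antibiotic duration. Nobody could treat a patient from it without turning to 8c and 8h.
3. It contains no statement that any group goes without saline.

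**Do the other passages agree with each other?** Yes, on this point. In step 4, the back-reference for Group 2 can only point to Group 1's list, which contains saline. The one for Group 3 reaches saline whichever earlier entry it points to. The wording of step 5 can be parsed with the background treatment belonging to all patients or to Groups 2 and 3; either way the prednisone groups have saline. The 8h list attaches no entry to a group, including the two prednisone courses, so saline's lack of a group there is only the format of the list.

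**The case for a change.** The strongest case for acting is that saline is a whole treatment component and not a parenthetical detail, so leaving it out is more than shortening a drug name. The contents of the arms belong in the protocol and cannot be left to a statistical analysis plan. Without a precedence rule, a reader is not told that 8c governs. Saline is also described as rinses for three weeks in one place and as free use in another. The repair would cost a few words, and it would protect the comparison on which the trial rests.

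Part of this stands. The two group-by-group lists do differ in wording for two of three groups, and the Section 6 sentence is untidy. A precedence rule, though, is needed only when two passages cannot both be followed. Here they can: giving treatment as 8c describes breaches nothing in Section 6. The confounding arises only if someone working from a recruitment entry treats an omission as an instruction to withhold, and disregards the objective, both procedure steps and the drug list. The difference between three weeks of rinses and free use does not bear on which groups receive saline.

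**Conclusion.** The textual difference is real, but it is a clerical omission and calls for no change to the plan. Section 6 names saline for one group of three. The objective and both relevant steps of 8c include it in the prednisone groups, and no passage withholds it. On those passages, the number of planned components separating each prednisone group from Group 1 is one; it would be two only if silence in Section 6 were taken as exclusion. No sample size, stated figure, comparison or analysis changes once the sentence is completed.

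This rests on two assumptions: that staff treat from the procedures and drug list, which alone carry doses and durations, and that the consent form and prescriptions, which are not shown, do not turn the omission into an instruction. It does not settle what the regimen should be. If the protocol is revised for other reasons, Section 6 can be reconciled with 8b and 8c by a cross-reference, with the sponsor confirming the arm description.
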